2.10 Unscheduled Visits

An unscheduled visit may be performed at any time during the study at the subject's request or as deemed necessary by the site Investigator. The date and reason for the unscheduled visit will be recorded in the source documentation.

2.11 Replacement of Subjects

Replacement of subjects who have withdrawn or been withdrawn from the study will be allowed to be replaced with prior approval from the sponsor and/or IRB.

2.12 Schedule of Visits and Procedures

	Visit #1*	Visit #2 - 5	Treatment Visit*** (Optional)	Call (Optional)	Visit #6	Visit #7
Procedure	Screening and Pretreatment Procedures	Treatment Visits 1-4 (1 - 2 weeks apart)	Treatment Visit #5 (2 - 3 weeks post last treatment)	Phone Call 1 Week Post Each Tx (1-7 Days)	Follow Up 4 Weeks Post Last Tx (+/- 1 Week)	Follow Up 12 Weeks Post Last Tx (+/- 1 Week)
Medical History	X					
Pregnancy Verification**	X	X	X			
Informed Consent	X					
Photographs	X	X	X		X	X
FWSS	X				X	X
Subject Pre-Treatment 1 Questionnaire		X				
Treatment		X	X			
Treatment Discomfort/ Pain Evaluation		X	X			
Subject Post Treatment 1 Questionnaire		X				
PGAIS					X	X
SGAIS					X	X
Subject Follow Up Questionnaire					X	X
Adverse Events Assessment	X	X	X	X	X	X

*Screening and Pretreatment Procedures may occur at the same time as the first Treatment Visit.

**Pregnancy verification required before each treatment only for women of childbearing potential.

***Group B only

2.13 Evaluation Methods

Photographs:

Photographs will be taken at baseline and at the 4 and 12 week follow up visit, and may be taken at eat treatment visit to assess the efficacy and safety of treatment.

Treatment Discomfort/Pain Evaluation:

Subjects will be asked to report the general level of treatment discomfort on a scale of 0 (none) to 10 (maximum intolerable pain) using the universal pain assessment tool (Appendix B)

Fitzpatrick Wrinkle Severity Scale

The Fitzpatrick Wrinkle Severity Scale will be used to evaluate outcomes. Live evaluation will be performed at Baseline and the 4 and 12 week follow up visits. The results will be compared to determine improvement.

Class	Wrinkling	Score	Degree of Elastosis
I	Fine wrinkles	1-3	Mild (fine textural changes with subtly accentuated skin lines)
II	Fine to moderate-depth wrinkles, moderate number of lines	4-6	Moderate (distinct papular elastosis [individual papules with yellow translucency under direct lighting] and dyschromia)
III	Fine to deep wrinkles, numerous lines with or without redundant skin folds	7-9	Severe (multipapular and confluent elastosis [thickened yellow and pallid] approaching or consistent with cutis rhomboidalis)

Subject Treatment Questionnaire:

Subject treatment questionnaires may be collected from each subject to obtain feedback on their treatment experience.

Blinded Evaluation:

Three blinded independent reviewers will perform a photographic evaluation in which they will be asked to identify pre-treatment images when compared to post treatment images. The reviewers will be Board Certified Dermatologists and/or Surgeons and will be chosen based on availability and have relevant clinical experience. They will attend a training session prior to grading.

Physician and Subject Questionnaire:

The Global Aesthetic Improvement Scale (GAIS) ranging from “worse” to “very much improved” will be used to judge the improvement as seen by the subject and Investigator.

Global Aesthetic Improvement Scale Assessment	
Rating	Description
1	Very Much Improved- Optimal cosmetic result in this subject

2	Much Improved- Marked improvement in appearance from the initial condition, but not completely optimal for this subject.
3	Improved- Obvious improvement in appearance from initial condition, but a re-treatment is indicated.
4	No Change- The appearance is essentially the same as the original condition.
5	Worse- The appearance is worse than the original condition.

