1.2 Objectives

1. Primary Objective:
 - Photographic evaluation with correct identification of pre-treatment 2D images when compared to the 12 week follow up images performed by three independent reviewers.
2. Assessments:
 - Photographic evaluation with correct identification of pre-treatment 2D images when compared to the 4 week follow up images performed by three independent reviewers.
 - Photographic evaluation with Fitzpatrick Wrinkle Severity Scale (FWSS) grading comparing pre-treatment images to the 4 and 12 week follow up images performed by three independent reviewers.
 - Principle Investigator assessment using the Global Aesthetic Improvement Scale (GAIS) at the 4 and 12 week follow up visit.
 - Subject assessment using the Global Aesthetic Improvement Scale (SGAIS) at the 4 and 12 week follow up visit.
 - Subject Questionnaires
 - Pre-Treatment 1
 - Post Treatment 1
 - Follow Up
3. Safety Objectives:
 - Collection of Adverse Events
 - Collection of Treatment Discomfort/Pain Evaluation

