2.2 Protocol Study Design

This is a prospective, open label, multi-center clinical study to collect efficacy data on the TempSure device and may also collect data on the Icon device.

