2.15.5 Analysis of Efficacy Variables

Additional efficacy variable is the change from baseline to Visit 7 (12 week follow up visit). Baseline is defined as the last assessment prior to the first treatment. The change from baseline to visits 6 and 7 will be analyzed using a Mixed Model Repeated Measures Analysis of Variance. A pairwise treatment group comparison at visit 7 will be performed using the results of this analysis. If a patient has no post-baseline assessment of the primary efficacy variable it will be assumed that the change from baseline to visit 7 is zero. The changes to visits 6 and 7 will be left as missing. Statistical significance with respect to the treatment group comparison at visit 7 will be declared if the two-sided p-value is < 0.05 . For each treatment group, summaries will be prepared for both the observed assessment and the change from baseline. The summaries will include the sample size, mean, median, standard deviation, minimum, and maximum. The statistical significance of the mean change from baseline for each treatment group will be determined using a paired t-test.

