3.2 Risk Management

The Investigator in this clinical trial has been invited to participate based on his/her previous experience with the use of the system and/or similar systems and industry experience. Experience with treatments is the most critical element in managing subject risk in this trial.

In addition, as with any study, there is a risk of bias. Objective evaluation methods may be used in conjunction with subjective evaluation methods when feasible. The value of the compensation to the clinical investigator for conducting the study is not influenced by the study outcome. If photographic results are listed as the primary objective, they are to be evaluated by blinded evaluators who did not partake in the study. If information concerning investigator assessment of improvement or investigator satisfaction is collected, then it is not listed as an objective for the study.

All other known risks will be disclosed to the subject via the informed consent process. Since this is an elective procedure and the subjects are volunteers, it can be assumed that their signature on the informed consent is indicative of their agreement to accept the risks involved.

The risks to the subjects who participate in this study are the same as those for the subject undergoing similar non-ablative radiofrequency treatment. It is possible to have an adverse reaction to the TempSure device use. There may be some side effects that we don't know about yet.

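### The objectives have FWSS graded from photographs by three independent reviewers, the methods have it graded live, and the analysis sections do not say which score is tested

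*Combined protocol and SAP*

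**What the plan says.** - **Section 1.2 (Objectives)** lists, among the assessments below the primary objective, "Photographic evaluation with Fitzpatrick Wrinkle Severity Scale (FWSS) grading comparing pre-treatment images to the 4 and 12 week follow up images", done by three independent reviewers.
- **Section 2.13 (Evaluation Methods)**, in its FWSS paragraph, says "Live evaluation will be performed at Baseline and the 4 and 12 week follow up visits" and that these results are compared to judge improvement. It names no grader. Its paragraph on blinded evaluation says "Three blinded independent reviewers will perform a photographic evaluation in which they will be asked to identify pre-treatment images when compared to post treatment images" and does not mention FWSS.
- **Section 2.12 (Schedule)** marks FWSS at Visits 1, 6 and 7. Photographs are marked at the same visits in a separate row.
- **Section 2.15.1** tests FWSS against a hypothetical no-change population without giving the source of the score.
- **Section 2.15.5** says "Additional efficacy variable is the change from baseline to Visit 7 (12 week follow up visit" and "The change from baseline to visits 6 and 7 will be analyzed using a Mixed Model Repeated Measures Analysis of Variance", followed by a paired t-test within each treatment group. It names neither the scale nor the rater.
- **Section 2.2** begins "This is a prospective, open label, multi-center clinical study".
- **Section 3.2** gives a conditional safeguard: "If photographic results are listed as the primary objective, they are to be evaluated by blinded evaluators who did not partake in the study".

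**The concern.** Sections 1.2 and 2.13 describe different measurements under one name. A photograph can be shown to a reviewer who does not know when it was taken. A live grading cannot be masked in that way, because the grader knows whether the visit comes before or after treatment.

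FWSS is the only wrinkle scale that the schedule records both before and after treatment; GAIS is recorded only at Visits 6 and 7. It is therefore the natural input to the change-from-baseline analysis in 2.15.5. There is no untreated arm, so a grader's expectation of improvement would appear in the mean change and could not be separated from an effect of the device. Section 2.1 says that the data are meant to support marketing claims, so it matters which score is reported.

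**Working it through.** **Comparing the sections**

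1. *Medium and rater.* Section 1.2: photographs, three independent reviewers. Section 2.13: live, grader not named. The two do not agree.
2. *Task of the blinded reviewers.* Section 2.13 gives them image identification only. Section 1.2 gives three independent reviewers both image identification and FWSS grading.
3. *Masking.* Section 1.2 does not call the FWSS reviewers blinded. Section 2.13 does so only for identification. The safeguard in 3.2 applies where photographic results are the primary objective, and FWSS is not primary. Masking of FWSS is therefore not secured under either description.
4. *Schedule.* The FWSS marks in 2.12 fall at visits where photographs are also taken, so they fit either description.
5. *Analysis.* Sections 2.15.1 and 2.15.5 do not name the source of the score, and neither says how three reviewers' scores would become one.

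**Illustration of size**

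The plan gives no expected FWSS change, SD or power, so it has no figure to reproduce.

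Inputs from the plan:
- The paired t-test is applied within each treatment group (2.15.5).
- At most 50 subjects are enrolled (2.1), and this number includes departures (2.15.2).
- The two-sided 0.05 level is stated for the group comparison in 2.15.5 and assumed here for the paired test.

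Assumed inputs:
- True change is zero.
- The rater shift b is 0.25 or 0.5 point on the 1–9 scale.
- The SD of change is 1.0, 1.5 or 2.0.
- There are 25 subjects per group, because the split between A and B is not given. All 50 in one group is the upper extreme.

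The noncentrality is δ = b / (SD/√n). The probability of significance is P(|T| > t*), where T is noncentral t with n − 1 degrees of freedom. The critical value t* is 2.064 for n = 25 and 2.010 for n = 50. For n = 25, b = 0.5 and SD = 1.0, δ = 0.5 / (1.0/5) = 2.5 and the probability is 0.67.

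| n in group | Rater shift | SD 1.0 | SD 1.5 | SD 2.0 |
|---|---|---|---|---|
| 25 | 0.5 | 67% | 36% | 22% |
| 25 | 0.25 | 22% | 13% | 9% |
| 50 | 0.5 | 93% | 64% | 41% |
| 50 | 0.25 | 41% | 21% | 14% |

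With no shift, each entry would be 5%. The smallest mean change that reaches significance is t* × SD/√n. For n = 25 this is 0.41, 0.62 or 0.83 point, and for n = 50 it is 0.28, 0.43 or 0.57 point.

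**The case against.** The strongest reply is that this is an additional assessment. The primary endpoint, identification of pre-treatment images, is done by blinded reviewers and does not depend on FWSS. That stands, and it limits the reach of the point. It does not remove the contradiction, because 2.15.1 sets a success condition on FWSS.

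A second reply is that live grading may be the better measurement. The scale in 2.13 includes elastosis features described under direct lighting, which a photograph may show less well. This is a fair argument about sensitivity. It does not answer the problem of a grader who knows the visit, and it is not what 1.2 says.

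A reader might also infer more than the documents support:

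- *That the plan promises blinded FWSS grading and then withdraws it.* Section 1.2 says independent, not blinded.
- *That the live grader is stated to be unmasked.* The grader is not named. Knowledge of the visit is inferred from the open-label design with every subject treated; the inference is strong, but it is an inference.
- *That two sets of FWSS scores will exist and the better one can be reported.* No section says that both are collected. One set described in two conflicting ways fits the text equally well. Selective reporting is a risk only if both are collected, in which case no priority is given.
- *That the n = 50 figures measure the problem.* The test is applied per group and 50 is a maximum, so those rows are an upper extreme.

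**Conclusion.** The point holds as an unresolved contradiction between 1.2 and 2.13, which 2.15.1 and 2.15.5 leave open. If 2.13 is followed as written, the wrinkle score comes from a grader who would know the time point, and its change mixes expectation with treatment effect. If 1.2 is followed, masking still has to be stated.

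The size depends on a rater shift and an SD that the plan does not give. At 25 per group, the illustrated false-positive rate runs from about 9% (0.25-point shift, SD 2.0) to 67% (0.5-point shift, SD 1.0). These figures show that a modest shift could decide the test; they do not estimate the bias in this study. The consequence is confined to the FWSS claim. It should be corrected, but it does not undermine the primary analysis.

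**What to change.** Reconcile 1.2, 2.12, 2.13, 2.15.1 and 2.15.5 so that they describe one analysed FWSS score. In line with the sponsor's own objective in 1.2, state that:

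- the analysed FWSS is the three reviewers' photographic grade;
- reviewers are masked to time point, with images unlabelled and in random order;
- the three scores are combined by a fixed rule, such as the mean;
- any live grade is supportive only, and its grader is named by role.

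The photographs and the three reviewers are already planned, and 2.13 already provides a training session. The added work is up to 50 subjects × 3 time points × 3 reviewers = 450 grades. The scientific cost is that photographs may detect less change than live grading. Keeping the live grade as supportive would let the sponsor see whether the two disagree.

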1.0 PURPOSE

1.1 Name and Intended Use

The device used in this study is called the TempSure device. The study will be using the Mini Envi handpiece and may also use the Envi handpieces and Icon device (Max series).

The intended use of the TempSure device used in this study to assess the efficacy of the handpiece for the treatment of facial wrinkles. If the Icon device is used, the intended use will be for the treatment of benign pigmented and/or vascular lesions.

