2.0 PROTOCOL

2.1 Protocol Methodology and Analysis

Methodology:

Subjects are to be enrolled in this clinical study if they are a healthy male or female 18 years of age or older. Up to 50 subjects will be enrolled at 3 study centers. Subjects will be enrolled into 2

groups, Group A for TempSure treatments only and Group B for TempSure and Icon treatments. Randomization will not be required as subjects will only be enrolled in Group B and treated with the Icon device if they present with pigment and/r vascular lesions. Subjects will attend a screening/pre-treatment visit which may be performed on the same day as the treatment visit. Subjects in Group A will receive up to 4 treatments with the TempSure device on the face. Subjects in Group B will receive 2 treatments with just the TempSure device and 2 treatments with both the TempSure and Icon device. Some subjects may be asked to return for an optional 5th treatment (2 – 3 weeks post last treatment) with the Icon device (and/or TempSure device) after the completion of their 4 treatments at the discretion of the Investigator. Subjects may receive a phone call 1 week (1-7 days) after each treatment to record side effects. Subjects will return for follow up visits at 4 and 12 weeks post last treatment for efficacy and side effects assessments. An unscheduled visit or phone call may be performed at any time during the study at the request of the subject or as deemed necessary by the site Investigator.

Analysis:

Upcoming generations are proving to have an interest in non-ablative aesthetic treatments and will drive demand for innovated products, procedures, and practice design.¹ Due to this shift in patient base, practices need to evolve to adapt to the newer generational ideologies. There have been rapid advances in RF technology over the past few years and the nonsurgical treatment using this energy source offers great promise to our aging population.² Radiofrequency technology for the treatment facial wrinkles and skin laxity needs to be further investigated to optimize treatment parameters for safe and effective non-ablative aesthetic treatments.

Relevance:

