2.8 Post Treatment Procedures

- Adverse events will be documented after treatment.
- Photographs may be taken post treatment.
- After treatment 1 only, subjects will be asked to complete a Post Treatment 1 Questionnaire.
- The following post treatment instructions will be reviewed:
 - If the skin is slightly pink or red in areas following the treatment, avoid hot water when washing or showering until any erythema (redness) has subsided.
 - Soothing creams or moisturizers, such as Aveeno, may be used.
 - Gently massage the treated area daily for 5 minutes for the duration of your involvement in the study.
 - Use a sun block with UVA and UVB protection with SPF of 30 or greater to prevent sun damage.
 - Maintain the same weight and exercise routine throughout the study.
- If the subject is treated with the Icon device, the following post treatment instructions will also be reviewed:
 - A mild sunburn-like sensation is expected. This usually lasts two to twenty-four (2-24) hours but can persist up to seventy-two (72) hours. Mild swelling and/or redness may accompany this, but it usually resolves in two to three (2-3) days. Apply wrapped ice or gel packs to the treatment area for ten to fifteen (10-15) minutes every hour for the next four hours, as needed. Never apply ice directly to skin. An oral, over-the-counter anti-inflammatory (ibuprofen such as Advil®) or an analgesic (acetaminophen such as Tylenol®) may be taken to reduce discomfort. Use medicine according to manufacturer's recommendations.
 - Until redness has resolved, it is recommended to avoid the following:
 - Applying cosmetics to treated areas.
 - Swimming, especially in pools with chemicals, such as chlorine.
 - Hot tubs, Jacuzzis, and saunas.
 - Activities that cause excessive perspiration or any activity that may raise core body temperature.
 - Sun exposure and tanning in treated areas. Apply a SPF 45 or greater sunscreen to prevent skin color changes.
 - Aggressive scrubbing and use of exfoliants on the treated area.
 - Bathe or shower as usual. Treated areas may be temperature-sensitive.

- Pigmented lesions may initially look raised and/or darker with a reddened perimeter.
- Pigmented lesions will gradually turn darker over the next twenty-four to forty-eight (24-48) hours. It may turn dark brown or even black.
- Pigmented lesions will progress to darkening and/or crusting and will start flaking off in an average of seven to twenty-one (7-21) days.

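### The FWSS score combines wrinkling with an elastosis column that names dyschromia in its 4-6 band, so pigment cleared by Icon can lower some Group B scores without any change in wrinkles

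*Combined protocol and SAP*

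**What the plan says.** **The scale.** The table in section 2.13 has a single Score column with bands 1-3, 4-6 and 7-9. Each band carries two descriptions. For 4-6, the wrinkling description is "Fine to moderate-depth wrinkles, moderate number of lines" and the elastosis description is "Moderate (distinct papular elastosis [individual papules with yellow translucency under direct lighting] and dyschromia". Dyschromia appears in neither the 1-3 nor the 7-9 row. Nothing says which column decides when the two disagree, and graders are not told to disregard pigment.

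**Its use.** Section 2.13 states: "The Fitzpatrick Wrinkle Severity Scale will be used to evaluate outcomes". It describes live grading at baseline and at weeks 4 and 12. Section 1.2 instead describes photographic grading by three independent reviewers, and lists FWSS under Assessments rather than as the primary objective.

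**The groups.** Section 2.1 says that "subjects will only be enrolled in Group B and treated with the Icon device if they present with pigment and/r vascular lesions". Section 1.1 says: "If the Icon device is used, the intended use will be for the treatment of benign pigmented and/or vascular lesions". Group A receives TempSure only. Section 2.8 tells Icon subjects that pigmented lesions "will start flaking off in an average of seven to twenty-one (7-21) days".

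**The analysis.** Section 2.15.5 models change from baseline to Visits 6 and 7, then says: "A pairwise treatment group comparison at visit 7 will be performed using the results of this analysis". The level is two-sided 0.05. A paired t-test within each group is also planned. Section 2.15.5 does not name its variable. Section 2.15.1 names FWSS among the scales to be tested, and in the schedule (2.12) FWSS is the only graded efficacy scale with a baseline assessment; both GAIS ratings appear only at follow-up.

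**The concern.** The study uses TempSure for wrinkles and Icon for pigmented and vascular lesions. An outcome meant to measure wrinkles should not respond to the removal of pigment, least of all when only one group has pigment removed. Here the score can respond, because one of its bands is partly defined by dyschromia.

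At stake is how a Group B result would be read. A fall in FWSS partly due to clearer pigment would be reported as wrinkle improvement in Group B. If FWSS is the variable in the Visit 7 comparison, it would also appear as a difference in wrinkle outcome between the groups. Section 2.1 says the data are meant to support marketing claims, so the distinction matters. Blinded grading does not remove the problem, since a blinded grader applying the printed table can still move the score. Baseline adjustment does not remove it either, because the artefact lies in the change itself. A single combined score cannot be split into its parts after grading.

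**Working it through.** **Step 1: can the score move with wrinkles fixed?** Set the rows of the 2.13 table side by side.

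| Band | Wrinkling column | Dyschromia named? |
|---|---|---|
| 1-3 | fine | no |
| 4-6 | fine to moderate depth, moderate number of lines | yes, with papular elastosis |
| 7-9 | fine to deep, numerous lines | no |

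Fine wrinkles are compatible with both of the first two rows, so the wrinkling column does not always separate a 3 from a 4. A subject with fine wrinkles and visible dyschromia could be given 4 at baseline. With the same wrinkles and less pigment, 3 becomes the natural choice. Within 4-6, a grader may also choose a lower value once the dyschromia has gone. The table gives no pigment-based reason to move within 1-3 or 7-9.

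**Step 2: is the artefact confined to one group?** Icon is given only in Group B, so Icon-driven clearance can occur only there. On timing, section 2.8 puts the start of flaking at 7-21 days on average. Visit 6 is 4 weeks after the last treatment with a 1-week window, so at the earliest day 21 (28 - 7). Visit 7 is at the earliest 11 weeks after (12 - 1). Both follow the expected onset of flaking, Visit 7 by a wide margin.

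**Step 3: how large could it be?** The plan gives no FWSS effect, SD, power or group split; section 2.15.2 gives only a total of 50. There is no plan figure to reproduce, so every input below except the level is an assumption.

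- 25 subjects per group, all evaluable.
- No true wrinkle change in either group.
- SD of change s = 1.0 point.
- A 1-point drop in a share q of Group B and none in Group A.
- Two-sided level 0.05, from 2.15.5.

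The Group B mean change is -q, and its variance is s² + q(1 - q). In absolute value, the expected test statistics are approximately:

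- between groups: q / √{[2s² + q(1 - q)] / 25}
- within Group B: q / √{[s² + q(1 - q)] / 25}

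For q = 0.50 these are 0.50 / √(2.25/25) = 0.50/0.300 = 1.67 and 0.50 / √(1.25/25) = 0.50/0.224 = 2.24. For q = 0.10 they are 0.10 / √(2.09/25) = 0.10/0.289 = 0.35 and 0.10 / √(1.09/25) = 0.10/0.209 = 0.48.

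Simulating 20,000 trials per setting, with a two-sample t-test between groups and a one-sample t-test of change in Group B, gives:

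| Share q | p < 0.05 between groups | p < 0.05 within Group B |
|---|---|---|
| 0% | 5% | 5% |
| 10% | 6% | 7% |
| 25% | 13% | 19% |
| 50% | 37% | 57% |

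**Sensitivity.** At q = 50%, moving the SD from 0.8 to 1.5 takes the between-group figure from 51% to 20% and the within-group figure from 72% to 33%. With a 35/15 split, q = 50% and SD 1.0, the figures are 34% and 36%. At q = 10% and SD 1.5 they are about 5.5% and 6.2%.

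**Cross-check.** A noncentral-t calculation with 25 per group and a uniform shift in Group B gives 0.14 and 0.23 for a 0.25-point shift, and 0.41 and 0.67 for a 0.5-point shift (SD 1.0). These are slightly higher than the simulation, as expected, because a uniform shift adds no variance.

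**The case against.** The strongest reply is that the route is narrow.

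- Dyschromia is named in one row only, joined to papular elastosis, and the same row has its own wrinkling description. A grader would have to let pigment tip the score. Where papular elastosis is present, clearing pigment does not remove it, and Class II may still fit.
- Group B may include subjects with vascular lesions only, for whom the dyschromia route may not exist. The documents do not equate a discrete pigmented lesion with the dyschromia in the table, and give no clearance rate.
- A grader who scores wrinkling alone avoids the problem.
- Near a 10% share, error rates are close to nominal.

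All of this stands, and it limits the size and the severity. It does not close the route, because fine wrinkles fit two rows and the plan does not require graders to let wrinkling govern.

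A reader might go further and infer any of three things that the documents do not support:

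- **That the table grades dyschromia throughout, so a typical Group B subject would drop a point.** It names dyschromia only in 4-6. Such a record is possible, but nothing shows it to be typical.
- **That the trial's success criterion is compromised.** The primary objective is correct identification of pre-treatment images, which does not use FWSS.
- **That the artefact alone stands between the data and a valid claim for adding Icon.** Allocation is by presenting lesions, not randomised, so the group comparison could not establish that benefit even with a perfect scale. Nor does 2.15.5 name FWSS; its use there is an inference from 2.12 and 2.15.1.

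**Conclusion.** The point holds as a measurement weakness in an additional assessment. As printed, the score can fall in some Group B subjects because pigment clears, mainly at the Class I/II boundary or within the 4-6 band. The bias favours apparent wrinkle improvement in Group B. It reaches the comparison at Visit 7 only if FWSS is the variable analysed in 2.15.5.

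The real size cannot be derived from the documents. Under the assumptions in the working (25 per group, SD 1.0, a 1-point artefact), it runs from close to the nominal 5% when a tenth of Group B is affected to 37% between groups and 57% within Group B when half is affected. The upper end needs many subjects to combine a pigmented lesion, a score at which pigment can count, a grader who lets it count, and clearance. Severity is low, but the matter has to be settled before grading.

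**What to change.** 1. In 2.13, have every FWSS grader record a 1-9 score from the Wrinkling column only, disregarding pigment and vascular change, and record elastosis/dyschromia as a separate item.
2. Reconcile 1.2 (photographic) with 2.13 (live), so that it is clear who grades. The training session in 2.13 is described only for the blinded photographic reviewers; if live graders score FWSS, the instruction must reach them too.
3. Use the wrinkling score for wrinkle claims in 2.15.1 and 2.15.5, and name it there. Report the elastosis item descriptively by group.
4. If comparability with other uses of the scale is wanted, keep the conventional combined score as a supportive summary.

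The cost is one grading instruction and one extra field. The drawback is that the wrinkling score is no longer the conventional combined scale, which item 4 partly offsets.
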